Individuals diagnosed with [Autism spectrum disorders](#) (ASD) often show patterns of restrictive and repetitive behaviors, reflecting a difficulty to inhibit excess sensory information in the brain. This information suggests sensory gating may be affecting some of the visible symptoms of ASD (Perry, Minassian, Lopex, & Lincoln (2007). Sensory gating describes neurological processes of filtering out redundant or unnecessary stimuli in the [brain](#) from all possible environmental stimuli, and prevents an overload of irrelevant information in the higher cortical centers of the brain. Current research on this topic is limited. An established method of evaluating brain activity is the use of event-related potentials (ERPs). ERPs are positive and negative voltage fluctuations (or *components*) in ongoing electroencephalograms (EEG) that are time-locked to the onset of a sensory, motor, or cognitive event. ERPs reflect brain activity that is specifically related to some stimulus or other event. ERPs are voltage fluctuations that are associated in time with some physical or mental occurrence. These potentials can be recorded from the human scalp and extracted from the ongoing electroencephalogram (EEG) by means of filtering and signal averaging (Picton et al., 2000). The results of EEG can be useful in documenting any changes in neural activity following the *ProFoveate™* intervention.

Protocol Summary

Specific Aims/Objectives

The purpose of this study is to document the effects of *ProFoveate™* intervention on the occurrence of self-stimulating behaviors and social skills in children diagnosed with high functioning autism spectrum disorders (HFASD). This study can potentially help researchers understand how to help reduce socially distracting self-stimulating behaviors in this group. There may even be evidence that changes in behavior may be reflected in changes in the brain.

The specific aim of this study is to:

1. Examine and describe the impact of the *ProFoveate™* intervention on parents' perceptions of self-stimulating behaviors and social interaction skills in their children diagnosed with HFASD and document any changes in brain activity.

TITLE: The Effects of *ProFoveate™* on Reducing Self- Stimulating Behaviors In Children Diagnosed With Autism Spectrum Disorders.
PI: [name]
Co-I: [name]

Specific Research questions are:

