1. Are there differences between the HFASD experimental and HFASD control group in the occurrence of self-stimulating behaviors as reported by caregivers, following *ProFoveate™* intervention?
2. Are there differences between the HFASD experimental and HFASD control group in social interaction skills as reported by caregivers, following *ProFoveate™* intervention?
3. Are there electrophysiological changes in the brains of individuals with HFASD in the control group compared to HFASD individuals in the experimental group, as measured by EEGs following *ProFoveate™* intervention?

The long term goal of this line of research is to determine if the supposition that the *ProFoveate™* intervention is beneficial to children with HFASD is substantiated by evidence from parent report of changes in self-stimulating behaviors and social interaction skills as well as by measures of change in neural activity in the experimental group. The first step in this process is to conduct a pilot study. Depending on the findings of this pilot study, future studies may be conducted with modifications to the procedures and more participants.

Test Article

Investigational Device

ProFoveate™ intervention for nystagmus is a management approach comprised of non-magnetic, 1.2 mm spheres that can be made from either stainless steel, gold or silver plated stainless steel or titanium, placed strategically about the face and ears and a set of exercises designed to support improved vision for patients with nystagmus. The spheres chosen for this study will be five pellet patches. We decided to use five pellet patches to ensure proper placement on the occiput with our target minor population. These multi pellet patches are 0.5" x 0.5" adhesive plasters that contain latex. Each patch features a geometrically spaced cluster of five 1.2 mm silver plated pellets. They are available from Lhasa OMS at <http://www.lhasaoms.com/> and come in packet of 50 pellets. We will give each participant one packet of 50 five pellet patches which will be enough for the study time frame. Any unused pellets will be returned. Individual patches (with adhesive tape) are removed from the backing as needed according to the prescribed treatment regimen. (See Figure 1)

Figure 1: *ProFoveate Five Pellet Patches* <http://www.lhasaoms.com/>

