To determine significance in the occurrence of self-stimulating behaviors or social skills following *ProFoveate*™ intervention nonparametric statistics will be run on questionnaire and test data obtained from the experimental and control groups. Test data will consist of pre and post treatment standard scores obtained from the test manuals and questionnaire data will consist of pre and post treatment summative Likert scores reported by parents. In order to gather ERP data, use of the STIM² software, SCAN EEG analysis software and associated hardware/peripheral devices (located in the Auditory Electrophysiological (Re)Habilitation Lab of the PI) for data gathering and analysis of the P300 ERP will be utilized for each participant. There are two independent variables: control group and experimental group. There are seven dependent variables: SSIS parent scores, SSIS student scores, TOPL-2 scores, blinded P50 measures, blinded P300 measures, Parent Questionnaire scores and blinded video ratings of self-stimulating behaviors (see supporting materials). Interjudge reliability for video ratings will be established by having two observers review 25% (8) of the video recordings, document the occurrence of self-stimulating behaviors and calculating the percent agreement. These scores will be triangulated to compensate for the fact that the parent ratings are not blinded. The data will be analyzed using a 2 (group) x 3 (standardized scores) x 1 (Physiological measure) x 2 (observational measures) repeated measures multivariate analysis of variance (See Figure 5).

Data Handling and Recordkeeping

All questionnaires and test forms will be maintained by the principal investigator in a locked file accessible only to the staff of the research study for three years. Both assessment sessions with students will be video recorded for later analysis of observable self- stimulating behaviors. Only the co-investigator and Citi-certified graduate students will view the videotapes. The videotapes and assessment protocols will be maintained in a locked file in the co-investigator's lab for three years and then destroyed.

Confidentiality

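### Triangulation is said to compensate for unblinded parent ratings, but it is only a consistency check: parent scores cannot on their own support a conclusion about occurrence of behavior

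*Protocol*

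**What the plan says.** The Statistical Plan opens with its purpose: "To determine significance in the occurrence of self-stimulating behaviors or social skills following" the intervention, "nonparametric statistics will be run on questionnaire and test data obtained from the experimental and control groups". It then defines one of those sources: "questionnaire data will consist of pre and post treatment summative Likert scores reported by parents". The blinded video rating is not among the data named there.

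Later the same section lists seven dependent variables, including the Parent Questionnaire, the SSIS parent scores and blinded video ratings. It sets a reliability check in which "two observers review 25% (8) of the video recordings", and continues: "These scores will be triangulated to compensate for the fact that the parent ratings are not blinded". The analysis is then given as a "2 (group) x 3 (standardized scores) x 1 (Physiological measure) x 2 (observational measures) repeated measures multivariate analysis of variance".

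Elsewhere the wording concerns perception. Under Specific Aims/Objectives, the aim is the impact on parents' "perceptions of self-stimulating behaviors and social interaction skills in their children diagnosed with HFASD". Research questions 1 and 2 ask about caregiver report, and the hypotheses in Study Design and Procedures are on parent perceptions. The long-term goal, stated after the research questions, seeks evidence of benefit from "parent report of changes in self-stimulating behaviors and social interaction skills as well as by measures of change in neural activity".

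**The concern.** Parents know the allocation. Study Design and Procedures gives the control group no intervention and no sham, and the treatment instructions and compliance sections have experimental-group parents learn the placement and record daily checks. The same parents complete the questionnaire and the SSIS Parent form before and after.

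A parent who expects improvement may score it without any change in the child. That is a true answer about perception and may be a false one about behavior. The Statistical Plan moves from the first to the second when it speaks of significance in occurrence. The compensation sentence is the only statement in the protocol on how the lack of blinding is handled. A reader of the results would be told that the problem had been offset when nothing described removes or bounds it.

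**Working it through.** **The text.** *These scores* may mean the video ratings just mentioned or all seven variables. On either reading, the operation places one set of scores beside another. If parents report improvement and the video does not, the comparison reveals a discrepancy. If both improve, it gives reassurance. In neither case does the parent-score difference between groups change. No weighting, correction, bound or decision rule is stated.

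The Parent Questionnaire is the only instrument in the questionnaire-and-test group that Study Design and Procedures describes as identifying self-stimulating behaviors. A nonparametric test of occurrence on those data is thus, for self-stimulating behavior, a test of a parent score.

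**Size, as an illustration.** The protocol states no alpha, SD, effect size or expectancy size, so there is no figure to reproduce. From the protocol: 15 per arm. Assumed: two-sided 0.05, normal scores, no device effect, a shift of *b* = 0.3, 0.5 or 0.8 SD in parent scores only.

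*One parent score, t-test.* Noncentrality = b × √(15/2) = 2.739b, with 28 df and critical value 2.048.

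| b (SD) | Noncentrality | t-test rejects | Rank-sum rejects (simulated) |
|---|---|---|---|
| 0.3 | 0.82 | 12.5% | 11.3% |
| 0.5 | 1.37 | 26.2% | 24.1% |
| 0.8 | 2.19 | 56.2% | 52.2% |

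*Joint test.* The layout has 3 + 1 + 2 = 6 slots for seven variables and the figure showing it is not available, so which scores enter is inferred. For a two-group MANOVA on change scores (Hotelling's T²) with *p* outcomes, noncentrality = (15/2) × δ′Σ⁻¹δ, referred to F(p, 29 − p). Example: six uncorrelated outcomes, both parent scores shifted 0.5 SD, gives 7.5 × (0.25 + 0.25) = 3.75 on F(6, 23), which rejects in 20.1%. The ranges below cover six or seven outcomes.

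| Parent scores included | b = 0.3 | b = 0.5 | b = 0.8 |
|---|---|---|---|
| Both (only they correlate, at 0.5 or 0.7; or all equal, 0 or 0.5) | 7–12% | 12–28% | 27–67% |
| One (all correlations equal, 0 or 0.5) | 7–9% | 11–18% | 23–43% |
| None | 5% | 5% | 5% |

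*Video alone.* In simulation its false-positive rate stayed at 4.7% to 5.4% whatever the parent shift.

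**What the video can detect.** At 80% power with 15 per arm, the detectable difference is 1.06 SD unadjusted (28 df). Adjusted for Visit 1 it is about 1.06 × √(1 − r²) (27 df): 1.01, 0.92 or 0.76 SD for an assumed baseline correlation *r* of 0.3, 0.5 or 0.7. The reliability check covers 8 recordings; with 30 children at two visits there could be 60, so 8/60 = 13%.

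**The case against.** The case for leaving the plan alone has real force. The protocol discloses that parent ratings are unblinded and never says the bias is corrected. To compensate may mean only to offset a weakness with other, blinded sources. The aim, questions and hypotheses are worded on caregiver report, so the opening of the Statistical Plan may be shorthand for research question 1. Video is a listed outcome with its own reliability check, P50 and P300 are also labelled blinded, and this is a pilot.

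Much of this stands, and it rules out stronger readings that a reader might infer:

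- *That parent scores have no bearing on occurrence, or that the plan rests on them alone.* The blinded outcomes are in the plan, and agreeing parent scores may corroborate a blinded result. The long-term goal also asks for neural evidence besides parent report.
- *That the research questions cannot be answered.* As worded, they can.
- *That the joint analysis is certainly contaminated.* That depends on an inferred layout.
- *That only parent ratings are exposed.* Children are shown the placement, wear the pellets and must be able to apply and monitor them. If they complete the SSIS Student form themselves, it is unblinded too. The calculations set every non-parent outcome to no shift and so ignore this route.

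The objection does not rescue the sentence. Offsetting a weak source with a stronger one requires saying which source carries the conclusion. The plan does not, and its statement on occurrence names the parent-scored data while omitting the video.

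**Conclusion.** The claim of compensation is wrong as written. Triangulation tests consistency; it leaves any expectancy shift in the parent scores. Those scores are valid for caregiver report and perception but cannot on their own support a conclusion that self-stimulating behavior occurs less often.

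This conclusion rests on the text and on the no-treatment control with parents who know the allocation. The false-positive rates (about 12%, 26% or 56% for one parent score, against a nominal 5%) show only what assumed shifts of 0.3, 0.5 or 0.8 SD would do, and the MANOVA figures depend also on the inferred layout. Relying on the video takes at face value the protocol's label that its ratings are blinded. The point should be corrected before results are interpreted; it does not undermine the trial's stated aim.

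**What to change.** In the Statistical Plan:

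1. Replace the compensation sentence with a statement that triangulation is a consistency check and does not remove bias from unblinded ratings.
2. Base any conclusion that the device reduces the occurrence of self-stimulating behavior on a between-group comparison of the blinded video ratings at Visit 3, adjusted for Visit 1, with parent scores as corroboration only.
3. Report the Parent Questionnaire and SSIS Parent scores as unblinded perception, answering research questions 1 and 2 as worded.
4. Do not cite a joint MANOVA that includes parent scores as evidence of a behavioral effect unless it is labelled as including unblinded ratings.
5. Treat the SSIS Student form, if completed by the child, as unblinded, and describe TOPL-2 as a measure whose assessor blinding is not stated.

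The cost is small: one baseline-adjusted comparison and revised labelling, with no new data, visits or research questions. The downsides should be stated. Video samples behavior in the clinic, not at home. Children admitted on visual characteristics may show little stereotypy on it (a floor effect), and observer agreement is checked on few recordings. Given the detectable differences above, a null video result is not evidence of no effect.

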1 will involve the initial assessments and visit 2 will involve the initial EEG. Visit 3 will involve final assessments and visit Child participants will be assessed using the following measures: 1) hearing screening at 25 decibels for the frequencies 1000, 2000 and 4000 hertz; 2) *Test of Nonverbal Intelligence* 3 (TONI-3; Brown, Sherbenou & Johnsen, 2009; 3) *Social Skills Improvement System SSIS* - Student form (Gresham & Elliot, 2008); and 4) *Test of Pragmatic Language* -2 (TOPL-2; Phelps-Terasaki & Phelps-Gunn, 2007; See Supporting Materials). All assessment procedures with each child in Visits 1 and 3 will be video recorded and analyzed using the observation of self-stimulating behaviors checklist (See Supporting Materials). Additionally, parent participants included in the study will assess their children using a standardize measure: 1) the *Social Skills Improvement System SSIS* - Parent form (Gresham & Elliot, 2008) and a non-standardized measure: 2) the *Questionnaire for Parents of Children with Autism Spectrum Disorders* ([name], 2013) (developed by the researcher to identify self-stimulating behaviors); to assess their children's social skills (See Supporting Materials). Both assessments will be administered at the beginning and end of the study. These assessments are expected to last 2 hours. The twenty-five self-stimulating behaviors identified as a concern for this study include: hand flapping, pulling or twisting ear, scratching, masturbating, shuffling or tapping feet, chewing clothes, picking or rubbing clothes, sucking finger, playing with hair, vocal noises, mouthing, self-injurious behaviors, head banging , rhythmic rocking, twirling objects, tongue rolling and clicking, teeth clicking, head shaking, knocking knees together, gazing at a particular object, repetitive rubbing of mouth and face, finger manipulations, locking hands behind head, grimacing , and tensing whole body and shaking.

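### The Statistical Plan gives four outcomes two unrelated analyses, and its MANOVA, the only analysis stated for the blinded outcomes, cannot be run as worded

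*Protocol*

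**What the plan says.** All in the protocol, section Statistical Plan, unless stated otherwise.

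- First rule: "nonparametric statistics will be run on questionnaire and test data obtained from the experimental and control groups". The section presents this as the way to establish significance for self-stimulating behaviors and social skills. It defines test data as pre and post standard scores and questionnaire data as pre and post Likert sums.
- Independent variables: "There are two independent variables: control group and experimental group".
- Outcomes: "There are seven dependent variables: SSIS parent scores, SSIS student scores, TOPL-2 scores, blinded P50 measures, blinded P300 measures", then "Parent Questionnaire scores and blinded video ratings of self-stimulating behaviors".
- Second rule, for the data as a whole: "2 (group) x 3 (standardized scores) x 1 (Physiological measure) x 2 (observational measures) repeated measures multivariate analysis of variance", with a reference to Figure 5, which is not in the text available for this review.
- ERP data: the named software and hardware are "for data gathering and analysis of the P300 ERP will be utilized for each participant". P50 is not mentioned in that sentence.
- Purpose of combining the measures: "These scores will be triangulated to compensate for the fact that the parent ratings are not blinded".
- Study Design and Procedures: "All assessment procedures with each child in Visits 1 and 3 will be video recorded and analyzed". ERPs are likewise recorded at the start and at the end. The hypotheses in that section speak of change and name both P50 and P300, each with peak and latency. The research questions ask about differences between the two groups.

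**The concern.** Two methods of different kinds, a set of nonparametric tests and a joint parametric model, apply to the same four outcomes, and their relation is not stated. The joint model is also not a design that an analyst could program. SSIS, TOPL-2, ERP and video scores are outcomes on different scales, not levels of a factor. The term that would carry the treatment effect, group by time, is not named. The number of measures does not match the list of outcomes two sentences earlier.

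This matters most for P50, P300 and the video ratings. They fall outside the nonparametric rule, so the MANOVA is all they have. Having one analysis per outcome is not itself a fault. The fault is that the one analysis is not usable as written, although these outcomes are the plan's safeguard against unblinded parent reporting.

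**Working it through.** **Count from the text**

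| Outcome | Nonparametric rule | MANOVA | Called blinded |
|---|---|---|---|
| SSIS parent | yes | yes | no |
| SSIS student | yes | yes | no |
| TOPL-2 | yes | yes | no |
| Parent Questionnaire | yes | yes | no |
| P50 | no | yes, if included | yes |
| P300 | no | yes | yes |
| Video ratings | no | yes | yes |

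Four of seven outcomes have two analyses; three have the MANOVA only. The MANOVA places are 3 + 1 + 2 = 6 against seven outcomes. The three standardized scores fit SSIS parent, SSIS student and TOPL-2. The two observational measures fit the Parent Questionnaire and the video ratings. One physiological place is then left for both P50 and P300.

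**Scale of the consequence**

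The protocol states no alpha, power, effect size or SD, so there is no figure of its own to reproduce. Only the 15 per arm comes from the protocol. The assumptions are: two-sided 5%, normal data, pre/post correlation r = 0.5, six measures with equal correlation c between outcomes (0, 0.3 or 0.5), and a true effect of 1.0 SD at the post visit on one outcome only.

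*Joint test (Hotelling T-squared).* F has 6 and 30 − 6 − 1 = 23 df. Noncentrality is (15 × 15/30) × D² = 7.5 D², with D² = (standardized effect)² × k. Here k is the diagonal element of the inverse correlation matrix, (1 + 4c)/((1 − c)(1 + 5c)) = 1.00, 1.26, 1.71.

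- Change: effect 1/√(2(1 − 0.5)) = 1, so D² = 1.00, 1.26, 1.71. Power 39/49/64%.
- Pre/post average: effect 0.5/√((1 + 0.5)/2) = 0.577, so D² = 0.33, 0.42, 0.57. Power 14/17/23%.

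*Single-outcome tests (noncentral t, noncentrality = standardized effect × √7.5).*

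- ANCOVA: 1/√(1 − 0.25) = 1.155, noncentrality 3.16, 27 df. Power 86% (79% at r = 0.3, 96% at r = 0.7).
- Change score: effect 1, 28 df. Power 75%.

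*When the joint test does better.* If all six outcomes move by 1.0 SD, D² on change is 6/(1 + 5c) = 6.0, 2.4, 1.71, giving 99.8/81/64%. It exceeds the 86% of a single ANCOVA only when the outcomes are weakly correlated.

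**False positives**

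- A t-test and a Mann-Whitney test of the same single outcome, counting either as a success: 5.8–6.1% in a null simulation with normal, heavy-tailed and skewed data.
- Seven separate tests at 5%: 1 − 0.95⁷ = 30% if independent, about 23% at outcome correlation 0.5 (simulation).

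**The case against.** The strongest reply is that the text says more than the concern allows.

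- A reader might infer that the plan is silent on which analysis decides. It is not quite: the opening sentence of the Statistical Plan ties the nonparametric tests to establishing significance, which gives them at least an apparent deciding role for research questions 1 and 2. But the MANOVA sentence then takes in all the data, so the relation is still unstated.
- A reader might infer that the pre/post contrast is missing altogether. The words repeated measures, the pre and post scores and the change hypotheses all point to a time term, and Figure 5 may show one. What stands is that the written factor list does not name it. The averaged reading is possible but less natural, so its low power should not be taken as what the plan intends.
- A reader might infer that double testing badly inflates false positives. On the same outcome it does not: about 5–6%. A six-outcome joint test and a one-outcome test answer different questions, so differing verdicts between them are not in themselves an error.
- This is a pilot, and a separate SAP may add detail. That covers omissions, but not a protocol section that gives six places to seven outcomes and writes outcomes as factors.

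**Conclusion.** The concern holds as a conflict within the Statistical Plan. Four outcomes have two analyses whose relation is not stated. The MANOVA is not an executable design, and it has six places for seven outcomes. The blinded ERP and video outcomes have no other stated analysis.

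These points need no assumptions. The power figures do: they rest on a 1.0 SD effect on one outcome, r = 0.5 and equal correlation between outcomes, and they show scale only. On the natural change reading, the joint test has 39–64% power against 86% for a baseline-adjusted test of the affected outcome at an unadjusted 5%. The point should be fixed. The documents do not support a claim that the pre/post comparison was forgotten or that the error rate is seriously inflated.

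**What to change.** 1. Replace both analyses with one stated analysis per outcome: the post score compared between groups by ANCOVA with the pre score as covariate, reporting the adjusted difference and its 95% CI. A permutation p-value for the group term is optional.
2. Apply it to the blinded video ratings and report them beside the Parent Questionnaire for research question 1, stating any disagreement. This gives the planned triangulation a defined form.
3. Remove the MANOVA and its count of measures, and bring Figure 5 into line. Word the hypotheses in Study Design and Procedures as between-group differences in baseline-adjusted post score, to match the research questions.
4. Reconcile P50. The hypotheses and the Statistical Plan list it, but the ERP procedures describe eliciting and measuring only P300. Either show that the recordings yield P50 or remove it.
5. Name one deciding outcome per research question and label the rest exploratory, or apply an adjustment such as Holm.

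Costs: for all outcomes except P50 this is rewording, since pre and post data are already scheduled; whether P50 needs anything more depends on item 4. The joint test is lost, with its advantage when all outcomes move together and are weakly correlated. Without item 5, seven 5% tests carry about a 23–30% chance of at least one false positive. Adjusting across all seven lowers power. With only one outcome affected, Holm in effect tests it at 0.05/7 = 0.0071, where the ANCOVA above (critical t 2.91, noncentrality 3.16, 27 df) has about 60% in place of 86%. One deciding outcome per question, each at 5%, keeps the 86%. The trial stays small either way: the 95% CI half-width is t(0.975, 27) × √(2/15) × √(1 − r²) = 0.71/0.65/0.54 SD for r = 0.3/0.5/0.7.
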